Study 2.1. Test whether 20Hz TI in the dACC enhances or disrupts cognitive control. For this, n=30 human subjects will be placed in the fMRI scanner to perform a flanker task(Eriksen & Eriksen, 1974), in which subjects must indicate whether the central arrow points left or right. The

trials will be 50% congruent (“<<<<” and “>>>>”) and 50% incongruent (“<<><<” and “>><>>”) trials. Previous work shows not only elevated reaction time and error rates for incongruent trials, but also a “Gratton effect” in which RT and error rate (as well as dACC activity) are even more elevated for incongruent trials that follow a previous congruent trial (Botvinick et al., 1999). This is arguably because cognitive control-related activity in the dACC prior to the start of the trial was lower, thus requiring more cognitive control-related activation as a reaction to the incongruent task stimulus(Botvinick et al., 1999). We will test whether the Gratton effect is reduced by TI to the dACC in the scanner, and whether this is accompanied by increased baseline dACC activity due to TI. Subjects will be divided into two groups. One will receive 2 consecutive eight-minute blocks of TI stimulation (2000 and 2020 Hz in the two electrode pairs, or alternatively the most effective beat frequency identified in Aim 1) to dorsal ACC, followed by 2 eight-minute blocks with no-TI stimulation, as subjects perform the flanker task in the fMRI scanner. The second group of subjects will undergo an identical procedure, except that the first two blocks will be no-TI stimulation, followed by 2 eight-minute blocks of TI stimulation. In all subjects, blocks 1 and 3 will include the Flanker task, and blocks 2 and 4 will include the visual search task of Magno et al., (2006). The visual search task will provide the data needed for Study 2.2.

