For Study 2.1, Behaviorally, we predict that the Gratton effect on both RT and error rate will be reduced in active TI vs. sham stimulation conditions. We will perform an ANOVA test with factors of on vs. off TI stimulation, previous trial congruent/incongruent, and current trial congruent/incongruent. We expect to find a significant interaction, with post-hoc tests showing reduced effects of previous trial congruency, and reduced interactions of previous trial congruency with current trial congruency. Neurally, we expect to find that the BOLD signal shows a main effect of increase during the TI stimulation vs. sham. Also, we expect to find that the contrast of dACC responses to incongruent minus congruent trials is attenuated in the active TI stimulation condition vs. no-TI. If so, we will conclude that TI disrupts cognitive control by attenuating the monitoring function of dorsal ACC. Potential problems and alternate approaches It is possible that TI stimulation here may enhance rather than disrupt neural function, in which case we may find larger rather than smaller Gratton effects with TI. In that case, we will ask whether the contrast of BOLD activity for incongruent minus congruent trials in dorsal ACC is correspondingly increased during active TI vs. sham stimulation.

For Study 2.2, behaviorally, we predict that TI will disrupt the dACC, leading to a smaller likelihood of skipping difficult trials. We will perform a logistic regression to determine how TI stimulation (on vs. off) and trial difficulty (easy vs. hard), and their interaction, predict the probability of skipping a trial. Neurally, we expect to find increased BOLD signal both for TI stimulation and for skipping a trial, in overlapping regions. Potential problems and alternate approaches As with Study 2.1, it is possible that TI stimulation here may enhance rather than

disrupt neural function, in which case we may find an increase rather than decrease in the probability of skipping with T1 stimulation. We will use two-tailed statistical tests to detect this possibility.

For Study 2.3, we will test whether T1 to dorsal ACC increases or decreases foraging probability, or alternatively, whether T1 reduces the reaction time differences of easy vs difficult decisions.

6.0 Statistical Analysis and Sample Size:

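### In Study 2.1's two-response flanker task the Gratton interaction is identical to the joint target-by-flanker repetition pattern, so behaviour alone cannot attribute a TI effect on it to conflict-driven control

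*Combined protocol and SAP*

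**What the plan says.** Section 3.0 (Study 2.1) defines the whole stimulus set: "trials will be 50% congruent (“<<<<” and “>>>>”) and 50% incongruent (“<<><<” and “>><>>”) trials". The response is binary: "subjects must indicate whether the central arrow points left or right". It describes the Gratton effect as reaction time and errors being "even more elevated for incongruent trials that follow a previous congruent trial", and sets the aim: "We will test whether the Gratton effect is reduced by TI to the dACC in the scanner".

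Section 5.0 gives the prediction, "we predict that the Gratton effect on both RT and error rate will be reduced in active TI vs. sham stimulation conditions", and the model: "We will perform an ANOVA test with factors of on vs. off TI stimulation, previous trial congruent/incongruent, and current trial congruent/incongruent". The expected post-hoc pattern includes "reduced interactions of previous trial congruency with current trial congruency". On the imaging side it expects that the "contrast of dACC responses to incongruent minus congruent trials is attenuated in the active TI stimulation condition vs. no-TI". If these predictions are borne out, section 5.0 will conclude that TI impairs cognitive control by weakening the monitoring role of the dACC.

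Neither section mentions a constraint on trial order, the exclusion of repeated displays, a repetition term in the model, or any limit on the cognitive-control conclusion.

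**The concern.** The Gratton effect is read as evidence that conflict on one trial adjusts control on the next. Successive trials can also share a target, a response or flankers, and such repetition may itself speed or slow responding. The behavioural test identifies control only if those repetition effects can be separated from the previous-by-current congruency interaction, or if TI leaves them unchanged.

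With four displays and two responses, one form of repetition cannot be separated at all. Aim 2 is meant to settle debates about the causal role of dACC, and section 5.0 commits to a specific mechanism. If TI altered the way repeated features are processed, the behavioural result would look the same as a change in control. Two-response data, once collected, cannot be corrected for this by later analysis.

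**Working it through.** **Inputs.** Four displays and two responses (section 3.0); the factors previous congruency, current congruency and TI (section 5.0). There is no figure in the plan to reproduce: the sample size in section 6.0 (25 required, 30 budgeted) is for a BOLD cluster, and that section says no behavioural effect sizes are available.

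**Step 1: the identity.** Code target *t* and flanker *f* as +1 or −1 for right or left. Congruency is *t·f*. Index the previous trial 0 and the current trial 1. Then

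previous × current congruency = (t₀f₀)(t₁f₁) = (t₀t₁)(f₀f₁) = T × F,

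where T = +1 if the target (and so the response) repeats and −1 if it changes, and F is the same for the flankers. This holds for every single transition, so it does not depend on trial order or display frequency. Multiplying both sides by the TI factor shows that the three-way term has the same alias. It applies to error rate as well as reaction time.

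**Step 2: enumeration.** There are 4 × 4 = 16 ordered pairs (lower case = previous trial, upper case = current trial):

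| Cell | Pairs | Exact repetition | Complete change | Partial repetition |
|---|---|---|---|---|
| cC | 4 | 2 | 2 | 0 |
| iI | 4 | 2 | 2 | 0 |
| cI | 4 | 0 | 0 | 4 |
| iC | 4 | 0 | 0 | 4 |

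The correlation of the interaction with the partial-versus-complete indicator is −1.0. Adding that indicator to intercept, previous, current and interaction gives five columns of rank 4. Adding T, F and T × F instead gives seven columns of rank 6.

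**Step 3: what is not aliased** (16 transitions equally likely).
- Response repetition alone and flanker repetition alone: each is 50% in every cell, correlation 0 with the interaction.
- Main effects of previous and of current congruency: correlation 0 with every repetition variable.
- Exact repetition alone: mean 1/4, variance 3/16, covariance with the interaction 1/4, so the correlation is 0.25/√0.1875 = 0.577 and the variance inflation is 1/(1 − 0.333) = 1.5. It is partly aliased, and separable.

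**Step 4: illustration with no control process.** Assume exact repetitions are *e* ms faster and complete changes *a* ms faster than partial repetitions. The cC and iI means each fall by (e + a)/2, so

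Gratton contrast = (cI − cC) − (iI − iC) = (e + a)/2 + (e + a)/2 = e + a.

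The simple contrast cI − iI is (e + a)/2. With exact repetitions dropped, the Gratton contrast is 2a.

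| e (ms) | a (ms) | All trials (ms) | Exact repeats dropped (ms) |
|---|---|---|---|
| 40 | 0 | 40 | 0 |
| 40 | 20 | 60 | 40 |
| 40 | 40 | 80 | 80 |
| 40 | −20 | 20 | −40 |

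If TI halved both benefits in the third row, the contrast would fall from 80 to 20 + 20 = 40 ms, and the analysis without exact repeats would show the same fall (2 × 40 to 2 × 20). With *a* = 0 and *e* between 20 and 60 ms, halving *e* would read as a reduction of 10 to 30 ms, but this would disappear once exact repeats were dropped. All these values are assumed.

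**Step 5: what removes the alias.** Dropping exact repetitions leaves 12 transitions, in which the interaction still correlates −1.0 with partial versus complete. Alternating a left/right set with an up/down set gives 2 × 4 × 4 = 32 possible transitions; 0 repeat the target or response and 0 repeat the flanker.

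**The case against.** The strongest reply is that the estimand is a within-subject difference between TI on and TI off. A repetition effect of equal size in both conditions cancels, so misattribution requires TI to change the target-by-flanker repetition effect specifically. Nothing in the documents shows that it does. Section 3.0 says about 66% of participants feel mild discomforts such as tingling, which leaves room for influences other than control, but that is not evidence of this one. The reply stands as far as it goes: a difference in the interaction can still be an effect of TI. It does not identify the mechanism, and the plan does not state the assumption that TI leaves repetition effects unchanged.

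Second, the conclusion in section 5.0 does not rest on the behavioural interaction alone. It also draws on the dACC incongruent-minus-congruent contrast and on effects of previous-trial congruency. The dACC contrast concerns the current trial and is not aliased. It is useful supporting evidence, but it says nothing about adjustment from trial to trial and does not remove the alias. The main effect of previous congruency is also unaliased. Its simple effect on incongruent trials (cI against iI) is not, since it compares partial with complete repetitions.

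Third, the task follows a cited paradigm, and changing it has a real cost in comparability. That stands.

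A reader might also infer a further confound from the congruent strings printing with four characters and the incongruent ones with five. The documents do not support this: a central arrow presupposes an odd number, so a typing or text-extraction slip is the likelier explanation.

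**Conclusion.** The alias is exact, but its scope is narrow. It concerns the joint pattern of target and flanker repetition, complete against partial, and it carries over to the TI interaction. It rests only on the four displays and two responses in section 3.0.

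Two stronger readings are tempting. One is that the Gratton effect is fully confounded with stimulus or response repetition of any kind. It is not: response repetition alone and flanker repetition alone are orthogonal to it, and exact repetition is separable. The other is that Study 2.1 cannot show a causal effect of TI. It can; what the behavioural data cannot show is that the effect works through conflict-driven control.

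The size of any distortion is unknown. The 20 to 60 ms range is assumed and illustrates exact-repetition priming only, which vanishes when exact repeats are dropped. The part that no analysis of this task can remove is complete change against partial repetition. This is a limit on interpreting one behavioural endpoint, with no safety consequence. It is worth correcting because the plan draws the mechanistic conclusion without qualification and later analysis cannot repair it.

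**What to change.** Before Study 2.1 data are collected, alternate left/right arrow trials with up/down arrow trials, so that no target, flanker or response from one trial can recur on the next. Keep 50% congruent trials, the block lengths and the ANOVA as planned. The cost is an edit to the task script, two more response keys and slightly more practice; the procedure summary already schedules practice for Aim 2. The change reduces comparability with the cited paradigm. It may also give a smaller Gratton effect, if repetition contributes to the usual one, and section 6.0 has no behavioural effect size against which to judge that loss.

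If the two-response task is kept, report the Gratton test both with and without exact repetitions. The second analysis loses half of the cC and iI trials and still leaves complete change aliased with partial repetition. Section 5.0 should therefore limit the behavioural conclusion to TI having changed the congruency sequence effect, and state that a repetition account is not excluded. That change of wording costs nothing.

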Study 2.2. Test the causal role of dorsal anterior cingulate in avoidance. We will apply TI stimulation as in Study 2.1 to the dorsal ACC with subjects in the fMRI scanner, and for efficiency, we will run this task on the same subjects as Study 2.1 concurrently and without leaving the scanner. Subjects will perform the task of Magno et al. (2006), during blocks 2 and 4 of the sessions described in Study 2.1. Specifically, subjects will perform a visual search task, identifying “target present” or “target absent” within a short deadline. There are two trial types, easy (few non-targets) and hard (many non-targets). They gain +1 reward for correct responses (converted to cash after the session), -1 reward for errors, and they can also skip the trial for 0 reward to avoid risk. Previous work shows dorsal ACC activity only when subjects skip the trial to avoid the risk of an error, but anterior insula activity occurs instead when subjects choose to respond and then make an error (Magno et al., 2006).

Study 2.3. Test the causal role of the dorsal ACC in foraging decisions. Using the TI stimulation of Study 2.1 with humans subjects in the scanner (n=30), subjects will perform a foraging and difficulty task(Shenhav et al., 2014) to adjudicate between competing theories of dorsal ACC, whether it drives foraging or reflects task difficulty. Subjects will be divided into two groups as in Study 2.1 and will perform the task of Shenhav et al. (2014)(Shenhav et al., 2014) during 4 eight-minute blocks, with TI and no-TI conditions in the scanner as in Study 2.1 for each of the two groups. In the task, subjects must decide whether to accept playing a gamble with known probabilities or forage to find a better gamble with more favorable probabilities. The relative value of foraging (RVF), i.e. the difference in expected value for playing the gamble vs. foraging, varies between an easy decision (large positive or negative RVF) or a difficult decision (near-zero RVF).

Risks of participation and mitigation of risks:

Subjects may feel uncomfortable completing the interview. For instance, there are questions about whether they may be pregnant, surgical history, and about the existence of tattoos and piercings on the body. They may decline to answer specific questions or decline to continue participating.

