While there is no evidence of increased risk with multiple scans, the risks associated with multiple scans are not known. The IUB imaging center is adopting an arbitrary maximum of 40 hours of scanning time per individual per year and the time involved in the present study is well below that limit.

Though uncommon, there is also the risk that the imaging procedure may result in nausea, dizziness, sweating, or headaches. Individuals who suffer from migraines may be more susceptible to these side effects as a result of the noise level inside the scanner. These symptoms are generally temporary, and the scan can be stopped at any time if you begin experiencing discomfort.

Brain stimulation:

1. Mild physical discomforts: Approximately 66% of participants who receive this kind of stimulation experience mild physical discomforts that are short-lived, such as tingling, itching, redness, or mild burning sensations on the skin under the pads. Some participants have also reported occasional mild headaches and fatigue. There is also a risk of seeing flashing lights.

These effects are mild, short lived, and benign. The electric current is very mild and is approximately 1000 times smaller than the average static electric shock one might receive touching a door knob or light switch after walking on a carpet with socks. While it is rare, some participants may experience a stronger unpleasant sensation. If subjects

experience any discomfort or wish to stop the experiment, subjects will let the experimenter know and the procedure will be stopped immediately.

2. Long term effects: Long term effects of exposure are largely unknown, though no long term adverse effects have been reported from any previous study. As a precaution, the stimulation will not last longer than 20 minutes continuously at one time.

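### Aim 2 is a single-session crossover with no stated washout: any TI after-effect falls on the TI-first group's comparator, most directly on Study 2.1's flanker block, and the planned models neither separate nor check it

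*Combined protocol and SAP*

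**What the plan says.** Section 3.0, Study 2.1, splits the subjects into two order groups. For the first, the plan reads "One will receive 2 consecutive eight-minute blocks of TI stimulation", "followed by 2 eight-minute blocks with no-TI stimulation, as subjects perform the flanker task in the fMRI scanner". For the second, "the first two blocks will be no-TI stimulation, followed by 2 eight-minute blocks of TI stimulation". Task positions are fixed: "In all subjects, blocks 1 and 3 will include the Flanker task, and blocks 2 and 4 will include the visual search task".

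Study 2.2 shares the session: "we will run this task on the same subjects as Study 2.1 concurrently and without leaving the scanner". Its search task runs "during blocks 2 and 4 of the sessions described in Study 2.1". Study 2.3, to be run only if time and resources allow, reuses the two-group TI and no-TI layout with a single foraging task in all four blocks.

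No washout or minimum interval is given. The study procedure summary at the end of 3.0 places a brief stimulation scale after each stimulation run, without a duration. It also assigns order by an alternating list, so about 15 of 30 subjects fall in each group.

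Section 5.0 specifies, for Study 2.1, an ANOVA with TI on/off, previous-trial congruency and current-trial congruency. For Study 2.2 it specifies a logistic regression on TI, difficulty and their interaction. Neither has a period or order-group term, and no first-period or order-specific estimate is planned.

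**The concern.** The comparison is within subject, so it relies on the no-TI blocks being free of TI's influence. In the no-TI-first group they are, because nothing active precedes them. In the TI-first group the flanker comparator is the first block after 2 × 8 = 16 minutes of TI block time. The search comparator comes after one intervening no-TI block.

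If TI effects outlast the current by minutes, that group's comparator partly resembles TI and the on-versus-off contrast shrinks. If there is a rebound, the contrast grows. Alternating the order does not help, because only one order has TI before its comparator. Aim 2 is meant to adjudicate between theories of dACC function, so either a null or a positive result could be misread. Section 6.0 says that no behavioural effect size is available for Aim 2, so there is no known margin to absorb a loss.

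**Working it through.** **The plan's own figures.** The plan gives no figure for after-effects. Its only sample-size figure (25 required, 30 budgeted) concerns the pilot BOLD contrast. The pilot effect size is not printed, so that figure cannot be reproduced, and it has no bearing on carry-over.

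**Inputs.** Block order and task positions come from 3.0, and n = 30 from 3.0 and 6.0. A 15:15 split follows from alternating allocation. Assumed: λ, two-sided 0.05 for Study 2.1 (two-tailed tests are stated for Study 2.2), and starting power.

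**Algebra.** Let T be the TI effect on the outcome (for Study 2.1, the change in the Gratton effect). Let p be the shift from the first to the second period, and λ the residue of TI in the following no-TI block, over and above any residue of no-TI. Each subject's TI minus no-TI difference has mean:

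- TI-first group: T − p − λ
- no-TI-first group: T + p

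With equal groups the average is T − λ/2, so p cancels and λ does not. The two group-specific effects differ by 2p + λ. With group sizes n1 (TI-first) and n2, and N = n1 + n2, the average is T − (n1/N)λ + ((n2 − n1)/N)p. Uneven attrition therefore lets part of p back in unless period is modelled. For the Study 2.2 logistic model the same reasoning holds approximately, on the log-odds scale.

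**Numbers.** Power is from a paired noncentral t with n = 30. The starting standardised effects, 0.53 and 0.61, are chosen to give 80% and 90% power when λ = 0.

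| λ/T (assumed) | Pooled estimate / T | Power if 80% at λ = 0 | Power if 90% at λ = 0 |
|---|---|---|---|
| −0.50 (rebound) | 1.25 | 94% | 98% |
| 0 | 1.00 | 80% | 90% |
| 0.10 | 0.95 | 76% | 87% |
| 0.25 | 0.875 | 69% | 81% |
| 0.50 | 0.75 | 56% | 68% |
| 1.00 | 0.50 | 29% | 37% |

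The gain in power in the rebound row comes from bias.

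**Simulation.** In 40,000 simulated trials with T = 1, a period effect of 0.3 and no period term, mean estimates were 1.00, 0.88, 0.75 and 0.50 for λ = 0, 0.25, 0.5 and 1.0. Power was 79%, 67%, 52% and 23%. It is below the table because the difference of 2p + λ between groups stays in the error term. A period term would recover that precision, but it would not remove the −λ/2 bias.

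**First-period comparison.** Block 1 for flanker, compared between groups at 15 vs 15, contains no λ. Its standardised effect is dz√(2(1 − ρ)), where dz is the paired effect and ρ the within-subject correlation. For assumed ρ from 0.8 to 0.3, power is 14% to 38% where the full design has 80%, and 18% to 48% where it has 90%.

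**The case against.** The strongest reply is that no after-effect has been shown. That is right. Every λ above is assumed, and the 50% loss is simply the formula at λ = T. A reader might take "Long term effects of exposure are largely unknown", in the brain stimulation risks of 3.0, as the plan admitting persistence. It is not: the statement is about long-term safety and says nothing about minutes-long effects on task performance. What stands is narrower. The design relies on zero carry-over without stating it, supporting it or providing a check.

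A reader might also infer that no-TI starts the instant that 16 minutes of current ends. The documents do not support this. A rating scale follows each stimulation run, and the 16 minutes is block time. The two-minute on/off cycle of Study 1.1 is not restated for Aim 2; if it applies, current is on for about 8 of the 16 minutes. Neither point changes the −λ/2 formula, though both bear on how large λ might be.

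A third tempting inference is that a null Study 2.1 beside a positive Study 2.2 would be explained by washout. The unequal distance from TI is real, but the tasks and outcomes differ, and the active search block also follows eight more minutes of TI block time than the active flanker block. No comparison between the two studies is planned. This is one possible explanation and no more.

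Finally, the available checks are weak. The no-TI-first group's own contrast is free of carry-over but estimates T + p, so practice or fatigue can pass for a TI effect. The first-period estimate is clean but imprecise. Both objections stand, and they limit the checks to descriptive use.

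**Conclusion.** The point holds conditionally. Aim 2 has no stated washout, the TI-first group's flanker comparator is the first block after TI, and the section 5.0 models have no order or period term. Any after-effect biases the pooled TI effect by −λ/2 under equal groups: towards the null if the residue resembles TI, away from it if there is a rebound. Assumed residues of 25%, 50% and 100% of the TI effect cost 12.5%, 25% and 50% of the estimate.

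The documents do not show that carry-over occurs, or how long it would last, so they do not support saying that Study 2.1 is biased. The flanker comparison is more exposed than the search comparison. Study 2.3, if run, shares the sequence problem but not the fixed task order. This is worth changing because the improvement is cheap; it does not invalidate the design.

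**What to change.** 1. In 3.0, place stimulation-free activities already in the 2–3 hour session between blocks 2 and 3, identically in both groups: the brief scale, and any non-task scans or task re-instruction. State the intended interval and record the actual one. The documents list no non-task scans, so the team must say what is available. Stimulation settings do not change.

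2. In 5.0, add period and order-group terms to the Study 2.1 and 2.2 models, and to 2.3 if run. They protect against uneven groups and recover precision. Say plainly that they do not remove carry-over.

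3. Pre-specify a descriptive sensitivity analysis: the first-period between-group estimate (block 1 for flanker, block 2 for search) with its confidence interval. Report the TI effect in each order group beside it, stating that each is confounded with period and that the two differ by twice the period effect plus carry-over. Do not use any of this as a pre-test or as a veto. Interpret null and positive pooled results alike in light of it.

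The cost is a few lines of text, slightly longer time in the scanner and no extra subjects. The first-period estimate, at about 15 vs 15, will be imprecise. Because the duration of any after-effect is unknown, the added interval may reduce carry-over without eliminating it.

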3. Medical precautions: Though a significant adverse event has never been reported with similar brain stimulation procedures, there theoretically may be a risk to persons with conductive metal (i.e. implants) in their head, and to persons who suffer from migraines, epilepsy, or other neurological syndromes. If subjects have any of these conditions they may be ineligible to participate in this study. Also, subjects may be ineligible to participate in the study if they have a history of seizure disorder, history of cognitive impairment, symptoms of psychosis or if you are taking medications for cancer, attention deficit hyperactivity disorder (ADHD), autoimmune deficiency syndrome (AIDS), or other mental illness.

These risks will be managed by trained researchers; at least one will always be present when the machine is operating. The researcher will stop the experiment if they experience discomfort that you do not wish to tolerate. Furthermore, the stimulator does not transfer current greater than 3 mA per electrode pair, which is still, relatively, a very small current.

Other risks

There is a small risk of boredom during the session. Subjects can withdraw themselves if they do not wish to continue.

There is also a small risk of loss of confidentiality. We will minimize that risk by storing the records in secure (locked or password-protected) locations. Electronic data will be identified only by the subject's study ID number, with the master list linking the subject ID to identifiable information stored on paper. Electronic data will be stored on the PI's servers or on Indiana University servers. All systems will have at least password protection. Paper data will be stored in locked cabinets inside a locked room.

Study procedure summary

Days before the session:

- Recruitment (via paper flyers and digital ads)
- Pre-screening (via phone)

Day of session:

- Consent
- Fill out questionnaires
 - MR safety screening
 - Demographic form
 - Edinburgh handedness inventory
 - WHODAS 2.0
 - PHQ-9
 - GAD-7
 - Stimulation experience scale (SES)
- Subjects randomized to receive active vs. sham stimulation first, using an alternating list, in which successive subjects are assigned to the conditions of active first, then sham first, then active first etc.
- Brief cognitive task explanation and practice (Aim 2 only)
- Attach electrodes (day of session, in MR facility)
- Scanning while undergoing TI (and if Aim 2, performing cognitive tasks) (day of session)

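### The Study 2.1 and 2.2 models list no period term, although within every Aim 2 subject TI versus no-TI is also first versus second performance of the task

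*Combined protocol and SAP*

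**What the plan says.** **Order and blocks.** Section 3.0 (Study 2.1) forms the Aim 2 groups thus: "Subjects will be divided into two groups. One will receive 2 consecutive eight-minute blocks of TI stimulation", followed by two blocks without TI. For the other group, "The second group of subjects will undergo an identical procedure, except that the first two blocks will be no-TI stimulation", and TI follows. The tasks have fixed positions: "In all subjects, blocks 1 and 3 will include the Flanker task", while the visual search of Study 2.2 is done "during blocks 2 and 4 of the sessions described in Study 2.1". Study 2.3, if run, keeps the scheme: "Subjects will be divided into two groups as in Study 2.1 and will perform the task".

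**Models.** Section 5.0 (Outcome Characteristics and Endpoint Definitions) says for Study 2.1: "We will perform an ANOVA test with factors of on vs. off TI stimulation, previous trial congruent/incongruent, and current trial congruent/incongruent". For Study 2.2 it names a logistic regression of skipping on stimulation, difficulty and their interaction. Neither list contains period, block, order or sequence, and section 6.0 adds no model terms. No model is named for Study 2.3.

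**How order is assigned.** The Study 2.1 text gives no rule for forming the groups. The only stated rule is in the Study procedure summary of section 3.0, which covers both aims: "Subjects randomized to receive active vs. sham stimulation first, using an alternating list". The same sentence spells out a fixed sequence beginning with active first: "using an alternating list, in which successive subjects are assigned to the conditions of active first, then sham first, then active first etc".

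**The concern.** Each subject has one early and one late block of each task, and stimulation changes exactly when period changes. Practice, fatigue or scanner adaptation between the two performances therefore enters that subject's TI minus no-TI difference. Reversing the order in the other group balances this in the average, but a model without period leaves it in the residual.

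What counts as a period effect differs by study. In Study 2.1 it is a change in the Gratton effect (the previous × current congruency interaction) between blocks 1 and 3. A change in overall reaction time alone does not touch that test. In Study 2.2 it is a change in the probability of skipping, particularly on hard trials.

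At stake are power and, with unequal groups, the size of the TI estimate. Section 6.0 states that there are no effect sizes for the Aim 2 behavioural outcomes, so no power margin has been shown that could absorb a loss.

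**Working it through.** The plan has no figure of its own to reproduce here: the 25 subjects in section 6.0 come from the pilot BOLD contrast, and no period effect is given.

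**Inputs from the documents.** 30 subjects per study, with 25 required (section 6.0); 200 recruits overall (section 3.0); two order groups; two-tailed tests (section 5.0, Study 2.2).

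**Assumptions.** Two-sided 0.05 throughout; TI effect τ = 0.5; Gratton change π from first to second performance of 0 to 1.0. Both τ and π are in units of the SD of the within-subject Gratton difference (TI minus no-TI).

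**1. Structure of the test.** The Study 2.1 test of TI × previous × current equals the squared one-sample t on each subject's Gratton difference D. The mean of D is τ + π when TI comes second and τ − π when TI comes first.

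**2. Bias without a period term.** Bias = π(n1 − n2)/n, where n1 is the TI-second group.
- 15/15: 0
- 13/12: 1/25 = 0.04 of π
- 14/11: 3/25 = 0.12 of π
- 15/10: 5/25 = 0.20 of π

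If 5 of 30 are lost at random from 15/15, the hypergeometric probabilities of these three unequal splits are 67%, 29% and 4%. The mean fraction is 0.67 × 0.04 + 0.29 × 0.12 + 0.04 × 0.20 ≈ 0.07. If the 200 recruits are spread evenly over five samples (40 each, an assumption) and 10 are lost at random from 20/20, 15/15 results 28% of the time, and the mean fraction is again 0.07.

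**3. Error term at 15/15.** The expected variance of D rises from 1 to 1 + (30/29)π². For π = 0.5 it is 1.26, so the standard error rises from √(1/30) = 0.183 to √(1.26/30) = 0.205. For π = 1.0 it is 2.03, and the standard error is 0.260.

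**4. Power at 15/15, τ = 0.5 (40,000 simulated trials per row).**

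| Gratton change π | Without period | With period |
|---|---|---|
| 0 | 75% | 75% |
| 0.25 | 74% | 75–76% |
| 0.5 | 67% | 75–76% |
| 0.75 | 57% | 75–76% |
| 1.0 | 44% | 75–76% |

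With only an overall reaction-time shift, power stays at 75–76% either way.

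**5. False positives, τ = 0, π = 1.0, no term.** Rejection is 0.7% at 13/12 and 3.7% at 15/10, so the test is conservative. At 20/10 it is about 17%, but losing all 10 of 40 from one group by chance has probability of about 0.04%. With the term, rejection is 5% at every split and the bias is 0.

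**6. Which term does the work.** At 15/10, adding only period × previous and period × current leaves the bias in TI × previous × current at 0.20 of π. It falls to 0 once period × previous × current is included.

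**7. Study 2.2.** Assumed: TI effect −0.4 log-odds on hard trials, 40 trials per TI × difficulty cell, random intercept SD 0.8, random TI slope SD 0.6, subject-clustered standard errors. Power at 15/15 without period is 76%, 69% or 43% for a shift of 0.2, 0.4 or 0.8 log-odds, against 76–78% with it. For a shift of 0.8 at 15/10 and no TI effect, the bias in TI is −0.138 with no term, −0.139 with an order-group main effect and 0.002 with period. If the shift is on hard trials only, the bias in TI × difficulty is 0.136 with period alone and −0.001 with period × difficulty. Section 5.0 does not list the clustering that these figures use. In 400 runs with no TI effect and no shift at 15/15, the listed terms without clustering rejected in 16.5%, against 6% with clustering.

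**The case against.** Four points can be made for the plan.

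- **The design already reverses order between the groups**, and alternation gives 15/15 at enrolment. This stands: a reader might infer that the Aim 2 TI effect is inevitably biased, and the documents do not support that. Bias needs unequal completers, and under random loss it averages only 0.07 of a period effect.
- **The period effect may be small.** Task explanation and practice precede Aim 2 scanning (section 3.0). This stands too. At 0.25 SD the loss is a point or two, and the 44% figure needs a change twice the assumed TI effect, for which no passage gives support.
- **Section 5.0 names factors of interest and may not be a full model.** It lists no subject term for Study 2.2 either. That is fair, but the silence is a reason to write the models out.
- **Alternation does little harm here.** A reader might infer selection bias as in a parallel-arm trial. The documents do not support that: every subject receives both conditions, and the procedure summary places the assignment of order after consent and the screening questionnaires. Alternation affects only who gets which order. What remains is that the rule is predictable and the label is wrong.

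**Conclusion.** The point holds as a cheap improvement to the model specification. In Aim 2, stimulation and period coincide within every subject, and the listed models for Studies 2.1 and 2.2 do not separate them. With equal groups the cost is a conservative test and lost power: about 1, 8 or 31 points in Study 2.1 for assumed Gratton changes of 0.25, 0.5 or 1.0 SD (75% to 74%, 67% or 44%). With unequal groups, 0.04 to 0.20 of the period effect remains in the TI estimate at splits from 13/12 to 15/10.

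All power figures rest on assumed TI and period effects, and those for Study 2.2 also on an assumed allowance for clustering within subject. A general claim of raised false positives would go too far: none appears up to 15/10, and 20/10 is very unlikely under random loss. The alternation label is a separate, minor matter of wording.

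**What to change.** Make these changes before Aim 2 data are seen.

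**Study 2.1 (section 5.0).** Add period (first or second time the task is done), period × previous, period × current and, essentially, period × previous × current. Only the last corrects the TI × previous × current test, so it should be named explicitly. Equivalently, enter order group as a between-subject factor with all interactions, sum-to-zero coding and Type III tests. An order-group main effect alone does not correct TI.

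**Study 2.2 (section 5.0).** Add period and period × difficulty, since the prediction concerns hard trials. State how repeated trials within subject are handled (random effects or subject-clustered standard errors).

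**Study 2.3, if run.** State a model and include the same period term.

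**Order assignment (section 3.0, Study procedure summary).** Call the rule alternation, or use a concealed, computer-generated permuted-block list. With random blocks of 4 and 6, 23% of lists of 30 end at 16/14. That leaves 2/30 = 0.07 of a period effect without the period term and none with it.

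**Cost.** One line per model and one sentence in section 3.0. In the Study 2.1 test the error degrees of freedom fall by one (29 to 28 at n = 30). If there is no period effect, no power is lost at 15/15 and about 2 points at 15/10 (67% to 65%). The term does not remove carry-over from TI into later no-TI blocks.
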